#### FBG=HI

- Emergent visit recommended in all cases
  - $\circ$  Patient willing to go  $\rightarrow$  arrange emergency transport
  - Patient not willing to go
    - Dispense medications based on 180(200)≤FBG<400 recommendations
    - Follow up in 1 day

#### PPBG=HI

- Patient is extremely sleepy or confused
- **No**

0

- Dispense medications based on 180(200)≤FBG<400 recommendations
- Follow up with FBG in 1-3 days
- $\mathsf{Yes} \to \mathsf{Emergency} \text{ visit recommended}$ 
  - Patient willing to go → arrange emergency transport
  - Patient not willing to go
    - Dispense medications based on 180(200)≤FBG<400 recommendations
    - Follow up later that day or the next day

# Appendix 11 - Month 3 Dosing Recommendations

#### A1c <5

→Confirm with repeat test. Stop medications, recheck A1c in 3 months

Version #: 1.0

[name]

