## 6.4 Route of Administration

All medications are administered by mouth. Patients will be treated with at least one of the three medications during the entire duration of the study and their participation in the diabetes treatment program (so, at least 6 months), aside from patients who may be observed off of medication to see if their diabetes is diet-controlled. Whether a patient is taking one of these medications or not depends on their individual characteristics, including glycemic control and targets, experience of side effects, and medication adherence, as described by the treatment protocols outlined below and in the appendices.

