### Monthly Visits

CHWs will meet with patients once per month to follow up on adherence and tolerance to medications, assess glycemic control, assess for complications of diabetes, refill medications (with dosing adjustments as needed for side effects, non-adherence or poor glycemic control), and provide diabetic education. These monthly visits will be facilitated by the smartphone application monthly protocol. This protocol mirrors the enrollment protocol as described above, with the following exceptions:

- Basic demographic information and medical history are not reassessed. This information is carried forward from the enrollment visit
- Blood glucose alone is collected. A1c is not collected unless it was recommended to be done the month
  prior and was not collected at that time
- Algorithms for medication adjustments are based on blood glucose, preferencing fasting glucose over postprandial glucose (Appendix 10)

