### Month 3 Visit

Version #: 1.0

[name]

At every 3rd monthly visit, starting with the visit 3 months after enrollment, A1c will be assessed. When A1c is checked, the month 3 medication titration algorithm (Appendix 11), is used rather than the monthly titration algorithm, which uses blood glucose. This protocol also considers the current glucose measurement to account for cases in which glycemic control may have improved significantly in the past month due to medication or lifestyle changes, but A1c may still be above goal due to earlier hyperglycemia. For example, if a patient with A1c goal of 7 has an A1c of 7.5, but FBG of 105, the application will recommend that the patient continues with the current medication dosing rather than recommending a dose increase. Other than checking A1c and using the A1c-based algorithm as indicated, the procedures performed at the month 3 visit are identical to those of the monthly visit.

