#### 5.7≤ A1c <6.5

- 1. Not taking medications → Patient has prediabetes. Counsel on diet and exercise and retest yearly
- 2. Nonadherent with medications  $\rightarrow$  May have diabetes. Stop medications and recheck A1c in 3 months
- 3. Taking metformin without problems
  - a. Metformin 500-1000 mg  $\rightarrow$  metformin 850 mg
  - b. Metformin 1500-2550 mg  $\rightarrow$  metformin 1700 mg
- 4. Taking metformin with problems
  - a. Metformin 500-850 mg, refuses to take metformin  $\rightarrow$  Stop medications, retest A1c in 3 months
  - b. Metformin 500-850 mg, agrees to take metformin  $\rightarrow$  metformin 850 mg
  - c. Metformin 1000-1700 mg  $\rightarrow$  metformin 850 mg
  - d. Metformin 2000-2550 mg → metformin 1700 mg
- 5. Taking glibenclamide, with or without hypoglycemia or hypoglycemia symptoms
  - a. All doses → metformin 1700 mg
- 6. Taking glibenclamide, previous problems with metformin, with or without hypoglycemia or hypoglycemia symptoms
  - a. All doses, agrees to take metformin  $\rightarrow$  metformin 850 mg
  - b. All doses, refuses to take metformin  $\rightarrow$  stop medications, recheck A1c in 3 months
- 7. Taking metformin and glibenclamide, with or without hypoglycemia or hypoglycemia symptoms
  - a. Metformin 500-1000 mg + glibenclamide any dose  $\rightarrow$  metformin 850 mg
  - b. Metformin 1500-2550 mg + glibenclamide any dose  $\rightarrow$  metformin 1700 mg

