#### 180(200)≤FBG<400 or 300≤PPBG<HI

- 1. Metformin without problems, adherent
  - a. Metformin 850 mg  $\rightarrow$  metformin 1700 mg
  - b. Metformin 1700 mg  $\rightarrow$  metformin 2550 mg
  - c. Metformin 2550 mg → metformin 2550 mg + glibenclamide 2.5 mg
- 2. Metformin without problems, nonadherent  $\rightarrow$  continue current doses
- 3. Metformin with problems, adherent
  - a. Metformin 850 mg, willing to continue → metformin 850 mg + glibenclamide 2.5 mg
  - b. Metformin 850 mg, not willing to continue  $\rightarrow$  glibenclamide 2.5 mg
  - c. Metformin 1700 mg  $\rightarrow$  metformin 850 mg + glibenclamide 2.5 mg
  - d. Metformin 2550 mg  $\rightarrow$  metformin 1700 mg + glibenclamide 2.5 mg
- 4. Metformin with problems, nonadherent  $\rightarrow$  same as #3
- 5. Glibenclamide without problems, no previous problems with metformin, took yesterday
  - a. Glibenclamide 2.5 mg  $\rightarrow$  metformin 1700 mg + glibenclamide 2.5 mg
  - b. Glibenclamide 5 mg  $\rightarrow$  metformin 1700 mg + glibenclamide 5 mg
  - c. Glibenclamide 10 mg  $\rightarrow$  metformin 1700 mg + glibenclamide 10 mg
- 6. Glibenclamide without problems, no previous problems with metformin, did not take yesterday
  - a. Glibenclamide 2.5 mg  $\rightarrow$  metformin 1700 mg
  - b. Glibenclamide 5 mg  $\rightarrow$  metformin 1700 mg + glibenclamide 2.5 mg
  - c. Glibenclamide 10 mg  $\rightarrow$  metformin 1700 mg + glibenclamide 5 mg
[name]

- 7. Glibenclamide without problems, previous problems with metformin, took yesterday
  - a. Agrees to take metformin  $\rightarrow$  metformin 850 mg + current glibenclamide dose
  - b. Refuses to take metformin
    - i. Glibenclamide 2.5 mg  $\rightarrow$  glibenclamide 5 mg
    - ii. Glibenclamide 5 mg  $\rightarrow$  glibenclamide 10 mg
    - iii. Glibenclamide 10 mg  $\rightarrow$  glibenclamide 10 mg
- 8. Glibenclamide without problems, previous problems with metformin, did not take yesterday  $\rightarrow$  same as #7
- 9. Glibenclamide with hypoglycemia symptoms, no previous problems with metformin, took yesterday
  - a. Glibenclamide 2.5 mg  $\rightarrow$  metformin 1700 mg
  - b. Glibenclamide 5 mg  $\rightarrow$  metformin 1700 mg + glibenclamide 2.5 mg
  - c. Glibenclamide 10 mg  $\rightarrow$  metformin 1700 mg + glibenclamide 5 mg
- 10. Glibenclamide with hypoglycemia or hypoglycemia symptoms, no previous problems with metformin, did not take yesterday → same as #9

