#### 5≤ A1c <6

- 1. Metformin without problems, adherent
  - a. Metformin 850 mg  $\rightarrow$  metformin 850 mg
  - b. Metformin 1700 mg  $\rightarrow$  metformin 1700 mg
  - c. Metformin 2550 mg  $\rightarrow$  metformin 1700 mg
- 2. Metformin without problems, nonadherent  $\rightarrow$  stop medications, recheck A1c in 3 months
- 3. Metformin with problems, adherent
  - a. Metformin 850 mg, refuses to take metformin → stop medications, recheck A1c in 3 months
  - b. Metformin 850 mg, agrees to take metformin  $\rightarrow$  metformin 850 mg
  - c. Metformin 1700 mg  $\rightarrow$  metformin 850 mg
  - d. Metformin 2550 mg  $\rightarrow$  metformin 1700 mg
- 4. Metformin with problems, nonadherent  $\rightarrow$  stop medications, recheck A1c in 3 months
- 5. Glibenclamide without problems, no previous problems with metformin, adherent
- a. All doses  $\rightarrow$  metformin 1700 mg
- Glibenclamide without problems, no previous problems with metformin, nonadherent → stop medications, recheck A1c in 3 months
- 7. Glibenclamide without problems, previous problems with metformin, adherent
  - a. All doses, agrees to take metformin  $\rightarrow$  metformin 850 mg
  - b. All doses, refuses to take metformin  $\rightarrow$  stop medications, recheck A1c in 3 months
- 8. Glibenclamide without problems, previous problems with metformin, nonadherent  $\rightarrow$  stop medications, recheck A1c in 3 months
- Glibenclamide with hypoglycemia or hypoglycemia symptoms, no previous problems with metformin, adherent → same as #5
- 10. Glibenclamide with hypoglycemia or hypoglycemia symptoms, no previous problems with metformin, nonadherent → stop medications, recheck A1c in 3 months
- 11. Glibenclamide with hypoglycemia or hypoglycemia symptoms, previous problems with metformin, adherent → same as #7
- 12. Glibenclamide with hypoglycemia or hypoglycemia symptoms, previous problems with metformin, nonadherent  $\rightarrow$  stop medications, recheck A1c in 3 months
- 13. Metformin and glibenclamide without problems, adherent
  - a. Metformin 850 mg + glibenclamide 2.5-5 mg  $\rightarrow$  metformin 850 mg
  - b. Metformin 850 mg + glibenclamide 10 mg  $\rightarrow$  metformin 1700 mg
  - c. Metformin 1700-2550 mg + glibenclamide 2.5-5 mg  $\rightarrow$  metformin 1700 mg
- d. Metformin 1700-2550 mg + glibenclamide 10 mg  $\rightarrow$  metformin 1700 mg + glibenclamide 2.5 mg 14. Metformin and glibenclamide without problems, nonadherent

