# Tx goal< A1c <9 AND FBG >130(150) OR PPBG >180(200

- 1. Metformin without problems, adherent
  - a. Metformin 850 mg  $\rightarrow$  metformin 1700 mg
  - b. Metformin 1700 mg  $\rightarrow$  metformin 2550 mg
  - c. Metformin 2550 mg  $\rightarrow$  metformin 2550 mg + glibenclamide 2.5 mg
- 2. Metformin without problems, nonadherent
  - a. Metformin 850 mg  $\rightarrow$  metformin 1700 mg
  - b. Metformin 1700 mg  $\rightarrow$  metformin 1700 mg
  - c. Metformin 2550 mg  $\rightarrow$  metformin 2550 mg
- 3. Metformin with problems, adherent
  - a. Metformin 850 mg, agrees to take metformin  $\rightarrow$  metformin 850 mg + glibenclamide 2.5 mg
  - b. Metformin 850 mg, refuses to take metformin  $\rightarrow$  glibenclamide 2.5 mg
  - c. Metformin 1700 mg  $\rightarrow$  metformin 850 mg + glibenclamide 2.5 mg
  - d. Metformin 2550 mg  $\rightarrow$  metformin 1700 mg + glibenclamide 2.5 mg
- 4. Metformin with problems, nonadherent  $\rightarrow$  same as #3
- 5. Glibenclamide without problems, no previous problems with metformin, adherent
  - a. Any dose  $\rightarrow$  metformin 1700 mg + glibenclamide current dose
- 6. Glibenclamide without problems, no previous problems with metformin, nonadherent

Version #: 1.0

[name]

- a. All doses  $\rightarrow$  metformin 1700 mg
- 7. Glibenclamide without problems, previous problems with metformin, adherent
  - Glibenclamide any dose, agrees to take metformin → metformin 850 mg + current glibenclamide dose
  - b. Refuses to take metformin
    - i. Glibenclamide 2.5 mg  $\rightarrow$  glibenclamide 5 mg
    - ii. Glibenclamide 5 mg  $\rightarrow$  glibenclamide 10 mg
    - iii. Glibenclamide 10 mg  $\rightarrow$  glibenclamide 10 mg
- 8. Glibenclamide without problems, previous problems with metformin, nonadherent
  - a. Willing to take metformin
    - i. Glibenclamide 2.5 mg  $\rightarrow$  metformin 850 mg
    - ii. Glibenclamide 5 mg  $\rightarrow$  metformin 850 mg + glibenclamide 2.5 mg
    - iii. Glibenclamide 10 mg  $\rightarrow$  metformin 850 mg + glibenclamide 5 mg
    - b. Refuses to take metformin  $\rightarrow$  continue current glibenclamide dose
- 9. Glibenclamide with hypoglycemia or hypoglycemia symptoms, no previous problems with metformin, adherent
  - a. Glibenclamide 2.5-5 mg  $\rightarrow$  metformin 1700 mg
  - b. Glibenclamide 10 mg  $\rightarrow$  metformin 1700 mg + glibenclamide 2.5 mg

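### The follow-up dosing tables have no row for a patient on no drug, so a patient stopped for low A1c or nonadherence gets no restart dose from them

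*Combined protocol and SAP*

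**What the plan says.** **Stops.** In Appendix 8 (enrollment), a nonadherent patient with A1c below 5.7 is taken off medication and retested in 3 months. For A1c 5.7 to below 6.5 the nonadherent row says: "May have diabetes. Stop medications and recheck A1c in 3 months". In Appendix 11 (the every-third-month visit), any patient with A1c below 5 gets "Confirm with repeat test. Stop medications, recheck A1c in 3 months". In its next band, A1c 5 to below 6, six nonadherent rows stop treatment, for example "Glibenclamide without problems, no previous problems with metformin, nonadherent → stop medications, recheck A1c in 3 months". Appendix 3 counts a patient who reports taking medication most of the time (75%) as nonadherent.

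**Patients off drug are expected.** Section 6.4 says that patients take at least one study drug throughout, "aside from patients who may be observed off of medication to see if their diabetes is diet-controlled".

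**Which table applies at follow-up.** Under Monthly Visits (7.4.2), "Algorithms for medication adjustments are based on blood glucose, preferencing fasting glucose over" postprandial readings, using Appendix 10. When A1c is checked, the Appendix 11 algorithm "is used rather than the monthly titration algorithm, which uses blood glucose". Neither section refers back to Appendix 8.

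**Where treatment is intensified.** In Appendix 10 this is the band "180(200)≤FBG<400 or 300≤PPBG<HI". In Appendix 11 it is the band headed "Tx goal< A1c <9 AND FBG >130(150) OR PPBG >180(200" and its counterpart for A1c 9 to 14.

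**Doses in the body text.** Section 2.6 puts patients with an initial or repeat A1c of 9 or more on both drugs. Section 6.5 starts metformin at 850 mg and raises it to 1700 mg after 2 weeks.

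**The concern.** A stop followed by a recheck in 3 months is a test of whether the patient needs treatment, so the table used at the recheck should say what to do when the answer is yes. Appendix 8 recognises an untreated patient and assigns a dose; the follow-up tables do not recognise one. The program rests on minimally trained CHWs acting at the visit on a concrete recommendation. For this patient the written tables supply neither a dose nor an instruction to call. What is at stake is delayed restart of oral therapy in a hyperglycemic patient whose drugs the plan itself withdrew, some of whom may have been taking three quarters of their doses.

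**Working it through.** The plan states no figure on this point. The check is a row count and a comparison of tables.

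**1. Stop entries for low A1c or nonadherence.**
- Appendix 8: A1c <5.7 row 2; A1c 5.7 to <6.5 row 2. That is 2.
- Appendix 11: the A1c <5 line, 1; A1c 5 to <6 rows 2, 4, 6, 8, 10 and 12, 6.
- Total 2 + 1 + 6 = **9**. Five of these name no drug problem: the two Appendix 8 rows, the A1c <5 line, and rows 2 and 6.

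Explicit stops of any kind number 12 in Appendix 8, 15 in Appendix 10 and 16 in Appendix 11, together 43. The other 43 − 9 = 34 follow refusal of metformin and are treated separately below.

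**2. Rows for a patient on no drug.**
- Appendix 10: 4 bands × 28 rows = 112. Appendix 11: 4 bands × 20 rows = 80. Of the 112 + 80 = **192**, none starts from a patient on no medication. Rows labelled nonadherent still start from metformin, glibenclamide or both.
- Appendix 8: 1 + 1 + 3 + 4 + 4 = **13** such rows across its five bands.

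**3. Where the gap matters.** For A1c, the test is whether Appendix 8 would start a drug in an untreated patient at the same level. For monthly glucose, it is the band in which section 2.7.2 allows up-titration.

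| Follow-up band | Rows | Off-drug rows | Why a start is expected |
|---|---|---|---|
| App. 10, FBG 180(200) to <400 or PPBG 300 to <HI | 28 | 0 | Section 2.7.2 allows monthly up-titration here |
| App. 11, A1c 6 to goal, when A1c ≥6.5 | 20 | 0 | App. 8, 6.5 to goal, rows 1–3 |
| App. 11, A1c above goal to <9, glucose raised | 20 | 0 | App. 8, goal to 9, rows 1–4 |
| App. 11, A1c 9 to 14, glucose raised | 20 | 0 | App. 8, 9 to 14, rows 1–4 |

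That is 28 + 20 + 20 + 20 = 88 rows, none of which fits. Two redirects widen the reach:
- Appendix 11 sends A1c above goal but <9 with controlled glucose to the 6-to-goal band.
- At monthly visits, Appendices 5 and 10 take the bridge dose, the declined-visit dose and the dose for an alert patient with PPBG reading HI from the first band in the table.

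**4. Worked cases.** Goal ≤7, nonadherent, enrollment A1c 6.2: stopped under Appendix 8. At month 3, with no metformin problems or hypoglycemia symptoms:
- A1c 7.5, FBG 150: raised-glucose band, no matching row. Appendix 8 gives an untreated patient at this A1c metformin 1700 mg.
- A1c 6.5 to 7: 6-to-goal band, no matching row. Appendix 8 gives metformin 1700 mg.
- A1c 8.8, FBG 125: redirected to the 6-to-goal band, no matching row. Appendix 8 gives metformin 1700 mg.

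**5. When referral would catch the patient.** Appendix 7 refers after 3 consecutive A1c values ≥9, or 4 above goal but <9. With checks at months 3, 6, 9 and 12, a patient stopped at enrollment qualifies at month 9 or month 12 at the earliest. Section 7.4.4 assures follow-up only to month 6. The referral for poor control on maximal doses cannot apply off drug.

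**6. Number affected.** Every Appendix 8 stop row requires A1c at or below goal. Section 8.1 assumes 13% at goal at baseline, so enrollment stops are at most 0.13 × 100 = 13 (0.13 × 150 = 19.5). This bound is loose: the two enrollment rows counted here need A1c <6.5 and nonadherence. The documents give no figure for stops during follow-up.

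**The case against.** The strongest reply is that the safeguards make this a completeness note. CHWs can telephone a coordinator or the medical director (2.1, 7.4.1). They are paired with a coordinator for the first several months after training (7.4.1). The physician reviews each visit, and any changes reach the patient, within 1 week. FBG of 400 or more prompts an urgent or emergent visit, A1c of 14 or more an urgent referral. Sections 2.6 and 6.5 state starting doses, and section 2.7.2 promises testing of every scenario. Some stopped patients may not have diabetes at all.

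All of this stands, and it limits the harm. It does not close the gap. The call depends on the CHW raising a question, and no row prompts it. The body-text doses are not carried into the follow-up tables for this patient. Scenario testing has no written expected result for a state that the tables omit.

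A reader might infer that all 43 stops lead to this gap. The documents do not support that. The 34 refusal stops may be caught by the intolerance referral (2.7.2, Appendix 7) or by withdrawal with prompt referral (5.7.2). A reader might also infer that the application malfunctions or that the CHW has no recourse. The documents show tables, not code, and the telephone route is explicit.

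**Conclusion.** The gap is real and should be fixed. Nine explicit entries create off-drug patients for low A1c or nonadherence, section 6.4 expects such patients, and 0 of 192 numbered follow-up rows covers them. The tables give no restart dose in four bands where the plan's own rules would start or intensify treatment, including A1c 6.5 to goal. The middle monthly glucose band is not part of the point, because section 2.7.2 plans no monthly up-titration there.

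The likely harm is a delay before physician review corrects the plan, in an unknown and probably small number of patients. The conclusion assumes that the application follows the written tables. It depends on no statistical input.

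**What to change.** Add off-medication rows to the follow-up tables.

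**Appendix 11**
- A1c <6.5: remain off medication, recheck A1c in 3 months.
- A1c 6.5 to goal: use Appendix 8, 6.5-to-goal band, rows 1–3.
- A1c above goal to <9: use Appendix 8, goal-to-9 band, rows 1–4. If glucose is controlled, the existing redirect leads to the 6.5-to-goal rows.
- A1c 9 to 14: use Appendix 8, 9-to-14 band, rows 1–4. If glucose is controlled, the existing redirect leads to the goal-to-9 rows.
- Where a reused row depends on the prescribed glibenclamide dose, use the last dose before the stop.

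A single remain-off line for the whole 6-to-goal band would be wrong. It would leave untreated a patient with A1c 8.8 and FBG 125 who is redirected there.

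**Appendix 10**
- FBG 180(200) to <400 or PPBG 300 to <HI: the medical director sets a restart dose or a mandatory same-visit call. The redirects in Appendices 5 and 10 then work without a text change.
- The three lower bands: remain off medication until the next scheduled A1c.

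Include the new rows in the scenario testing of section 2.7.2. The cost is a small amendment plus application programming and testing, with no extra visits, tests or staff.

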#### 5≤ A1c <6

- 1. Metformin without problems, adherent
  - a. Metformin 850 mg  $\rightarrow$  metformin 850 mg
  - b. Metformin 1700 mg  $\rightarrow$  metformin 1700 mg
  - c. Metformin 2550 mg  $\rightarrow$  metformin 1700 mg
- 2. Metformin without problems, nonadherent  $\rightarrow$  stop medications, recheck A1c in 3 months
- 3. Metformin with problems, adherent
  - a. Metformin 850 mg, refuses to take metformin → stop medications, recheck A1c in 3 months
  - b. Metformin 850 mg, agrees to take metformin  $\rightarrow$  metformin 850 mg
  - c. Metformin 1700 mg  $\rightarrow$  metformin 850 mg
  - d. Metformin 2550 mg  $\rightarrow$  metformin 1700 mg
- 4. Metformin with problems, nonadherent  $\rightarrow$  stop medications, recheck A1c in 3 months
- 5. Glibenclamide without problems, no previous problems with metformin, adherent
- a. All doses  $\rightarrow$  metformin 1700 mg
- Glibenclamide without problems, no previous problems with metformin, nonadherent → stop medications, recheck A1c in 3 months
- 7. Glibenclamide without problems, previous problems with metformin, adherent
  - a. All doses, agrees to take metformin  $\rightarrow$  metformin 850 mg
  - b. All doses, refuses to take metformin  $\rightarrow$  stop medications, recheck A1c in 3 months
- 8. Glibenclamide without problems, previous problems with metformin, nonadherent  $\rightarrow$  stop medications, recheck A1c in 3 months
- Glibenclamide with hypoglycemia or hypoglycemia symptoms, no previous problems with metformin, adherent → same as #5
- 10. Glibenclamide with hypoglycemia or hypoglycemia symptoms, no previous problems with metformin, nonadherent → stop medications, recheck A1c in 3 months
- 11. Glibenclamide with hypoglycemia or hypoglycemia symptoms, previous problems with metformin, adherent → same as #7
- 12. Glibenclamide with hypoglycemia or hypoglycemia symptoms, previous problems with metformin, nonadherent  $\rightarrow$  stop medications, recheck A1c in 3 months
- 13. Metformin and glibenclamide without problems, adherent
  - a. Metformin 850 mg + glibenclamide 2.5-5 mg  $\rightarrow$  metformin 850 mg
  - b. Metformin 850 mg + glibenclamide 10 mg  $\rightarrow$  metformin 1700 mg
  - c. Metformin 1700-2550 mg + glibenclamide 2.5-5 mg  $\rightarrow$  metformin 1700 mg
- d. Metformin 1700-2550 mg + glibenclamide 10 mg  $\rightarrow$  metformin 1700 mg + glibenclamide 2.5 mg 14. Metformin and glibenclamide without problems, nonadherent
- a. Metformin 850 mg + glibenclamide any dose  $\rightarrow$  metformin 850 mg
  - a. Metorian 000 mg  $\cdot$  gibericiande any 003e  $\rightarrow$  metorian 000 mg
  - b. Metformin 1700-2550 mg + glibenclamide any dose  $\rightarrow$  metformin 1700 mg
- 15. Metformin and glibenclamide, problems with metformin, adherent
  - a. Agrees to take metformin
    - i. Metformin 850 mg + glibenclamide 2.5-5 mg → metformin 850 mg
    - ii. Metformin 850 mg + glibenclamide 10 mg  $\rightarrow$  metformin 850 mg + glibenclamide 2.5 mg b. Refuses to take metformin
      - i. Metformin 850 mg + glibenclamide 2.5 mg  $\rightarrow$  stop medications, recheck A1c in 3 months
      - ii. Metformin 850 mg + glibenclamide 5 mg → glibenclamide 2.5 mg
      - iii. Metformin 850 mg + glibenclamide 10 mg  $\rightarrow$  glibenclamide 5 mg
    - c. Metformin 1700 mg + glibenclamide 2.5-5 mg  $\rightarrow$  metformin 850 mg

Version #: 1.0

